#### 4.5.2 Discontinuation of all or part of the study

Given that this study investigates standard practice, no study discontinuation criteria have been defined in advance, except the following:

1. scientific publication resulting in a consensus that challenges the primary study hypothesis or the method used to treat mechanically ventilated patients;
2. interim analysis conducted by the independent data monitoring committee and showing an early significant difference in the primary endpoint .

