The lower intestinal tract can also be the site of complications characterized by ischemia despite patency of the blood vessels, a condition known as nonocclusive mesenteric ischemia (NOMI) (55). NOMI may affect 20% to 30% of ICU patients with severe circulatory failure. Intense splanchnic vasoconstriction designed to preserve blood flow to essential organs (the brain, heart, and kidneys) can result in necrotizing enterocolitis, a condition that is fatal in 70% to 100% of cases (56, 57). The main causative factors are medications (catecholamines, vasoconstrictors, cardiovascular drugs), patient characteristics (chronic hemodialysis, heart surgery, multiple trauma), and critical complications (acute respiratory distress syndrome, septic shock, cardiogenic shock, fluid and sodium overload) (58-60). The potential role for enteral nutrition in the development of NOMI remains controversial. A study involving superior mesenteric artery blood-flow measurement 3 h after the introduction of nutritional support in volunteer ICU patients failed to conclusively resolve this issue (61). Enteral nutrition was associated with a greater than 50% blood-flow increase and parenteral nutrition with a greater than 60% decrease, indicating a theoretical risk of a mismatch between oxygen supply and demand in the splanchnic territory in patients with acute circulatory failure receiving enteral nutrition.

Another contributor to the current underuse of early enteral nutrition in many patients is the conflicting nature of findings from available studies. In addition, no study to date has demonstrated that a specific nutritional modality is associated with decreased mortality.

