## 4) STUDY CONCEPTS

### 5.13 Detailed descriptions of the primary endpoint and, where applicable, of the secondary endpoints

#### 4.1.1 Primary endpoint

The primary endpoint is all-cause mortality by day 28 (D28). Information on this endpoint will be collected on the 28th day after inclusion of the patient in the study. For patients who have been discharged, information on the primary endpoint will be collected by a telephone call to the patient at home.

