## 7.4 Statistical rules for study discontinuation

We will perform two interim analyses, after inclusion of the first 1000 and the first 2000 patients, respectively. We will use Peto's boundary (*Peto R, Pike MC, Armitage P, et al. Design and analysis of randomized clinical trials requiring prolonged observation of each patient. I. Introduction and design. Br J Cancer 1976;34:585-612. PMID*):

- the significance level associated with the first interim analysis is 0.01;
- the significance level associated with the second interim analysis is 0.01;
- the significance level associated with the final analysis is 0.049.

This method yields an overall Type I error of 5%.

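### The plan specifies no interim review of bowel ischemia and lists no safety reason to stop, and the interim mortality test is nearly blind to an ischemia excess of a few points.

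*Combined protocol and SAP*

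**What the plan says.** Section 4.5.2 reasons that the trial studies standard practice and therefore states that "no study discontinuation criteria have been defined in advance, except the following". Two items follow. One is a "scientific publication resulting in a consensus that challenges the primary study hypothesis" or the way ventilated patients are treated. The other is an "interim analysis conducted by the independent data monitoring committee and showing an early significant difference in the primary endpoint". Section 4.1.1 defines the primary endpoint as all-cause mortality by day 28.

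Section 7.4 places the two interim analyses "after inclusion of the first 1000 and the first 2000 patients, respectively". On the levels it says that "the significance level associated with the first interim analysis is 0.01" and that "the significance level associated with the second interim analysis is 0.01". It names no safety variable.

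The harm in question is the protocol's own. The synopsis rationale says that enteral feeding in circulatory failure may induce nonocclusive mesenteric ischemia. The overview of the research project (section 2 of the protocol) describes the resulting necrotizing enterocolitis as "a condition that is fatal in 70% to 100% of cases" and calls the role of enteral nutrition controversial. Documented bowel ischemia is a secondary endpoint (4.1.2), to be compared with the method used for the primary analysis (7.1.4). No interim use of it is stated.

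**The concern.** Section 4.5.2 reads as a closed list. Followed as written, an excess of bowel ischemia in the enteral arm is not a listed reason to pause or stop unless it produces a significant mortality difference. An uncommon event moves all-cause mortality only slightly, even when it is usually fatal, and background mortality is assumed to be 37%. A real excess of a few percentage points could therefore pass both looks unnoticed if the committee relies on the mortality test alone. If enteral feeding also lowered mortality in other ways, as the trial hopes, the signal would be hidden further. The patients at stake are those allocated to enteral feeding after each look.

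**Working it through.** **Inputs from the documents.** Day-28 mortality 37% (parenteral) and 32% (enteral), final alpha 0.049, power 80%, 1427 per group (7.2). Looks at 1000 and 2000 patients, taken as 500 and 1000 per arm, at level 0.01 (7.4). Fatality of mesenteric ischemia 70% to 100% (synopsis; overview of the research project). The only incidence figure is 20% to 30% in ICU patients with severe circulatory failure (same overview), and it is not split by arm.

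**Assumptions.** Ischemia rates by arm, which the documents do not give, and two-sided tests, which is the variant that reproduces the sample size.

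**Step 1. The plan's own figure.** n = [1.969·√(2·0.345·0.655) + 0.842·√(0.37·0.63 + 0.32·0.68)]² / 0.05² = 1426.5, rounded up to 1427 per group. It reproduces.

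**Step 2. Mortality difference needed to cross 0.01.** 2.576·√(2·0.345·0.655/n) gives 7.7 points at 500 per arm and 5.5 points at 1000 per arm.

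**Step 3. Chance that the mortality test flags enteral harm.** Let ΔI be the excess ischemia rate and f the fatality. Excess mortality is δ = ΔI·f if every ischemia death is additional, or δ = ΔI·(f − 0.37) net of background deaths. The probability is P(Z > [2.576·SE₀ − δ]/SE₁), where SE₀ is the pooled and SE₁ the unpooled standard error.

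Example: 1% vs 3%, f = 1, all deaths additional, 500 per arm. δ = 0.02 and SE₀ = √(2·0.38·0.62/500) = 0.0307, with SE₁ about the same. Then (2.576·0.0307 − 0.02)/0.0307 = 1.92, so the probability is 2.7%.

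**Step 4. Direct comparison of ischemia at 0.01** (an illustrative level), by uncorrected chi-square and by Fisher's exact test, counting only results with enteral worse.

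| Ischemia, parenteral vs enteral (assumed) | Mortality test, look 1 / look 2 | Chi-square on ischemia | Fisher on ischemia |
|---|---|---|---|
| 1% vs 2% | 0.7% / 0.8% to 1.2% / 1.7% | 8.2% / 21.6% | 5.5% / 17% |
| 1% vs 3% | 0.9% / 1.2% to 2.7% / 4.9% | 37% / 75% | 30% / 70% |
| 20% vs 30% (extreme) | 6.6% / 14% to 74% / 97.5% | not computed | not computed |

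In the mortality column the lower pair is 70% fatality net of background and the upper pair is 100% fatality with all deaths additional. With no effect at all, the mortality test flags harm 0.5% of the time per look.

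**Step 5. Masking.** If enteral feeding otherwise gave the assumed 5-point benefit, an ischemia excess of up to 4 points with total fatality would flag harm with probability 0.2% or less per look.

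**Step 6. What an interim review could prevent at most.** At 3% vs 1%, excess cases still to come are (1427 − 500)·0.02 = 18.5 after look 1 and (1427 − 1000)·0.02 = 8.5 after look 2. At 2% vs 1% they are 9.3 and 4.3. These are ceilings, since a review must also lead to action.

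**The case against.** Several points on the other side stand in whole or in part.

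- *A reader might infer that the committee never sees ischemia data.* The documents do not say that. They are silent on what the committee receives beyond the primary endpoint, and the contents list shows a section 1.2 on coordination and monitoring whose text is not in the version available here. A remit could be set out there. If so, it would still have to be reconciled with the closed list in 4.5.2.
- *A reader might infer that the mortality test cannot see ischemia at all.* That holds for an excess of a few points. At 20% vs 30% it ranges from poor to good, depending on fatality and on how many of those patients would have died anyway.
- *A reader might count about 29 excess cases over the whole trial* (1427·0.02 = 28.5 at 3% vs 1%). That includes about 500 enteral patients enrolled before the first look, whom no interim review could protect. Converting all cases to deaths at 70% to 100% also ignores the 37% background.
- *Direct comparison is not strong either.* At 1% vs 2% it has low power at both looks. This argues for showing the committee the counts, not for a formal boundary.
- *The endpoint may miss the harm.* The imaging route in 4.1.2 requires absent flow in a main artery, whereas the overview describes ischemia despite patent vessels. Section 4.6 lists no dedicated bowel-ischemia item, only an abdominal complication among the reasons for reducing or stopping feeding. Usable data at the first look are therefore not assured.
- *Both arms are standard care*, and the protocol asserts no added risk. That explains the choice, but it does not answer a specific hazard that the protocol itself raises for these patients.

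**Conclusion.** The point holds in a limited form. The only listed reasons to stop are an outside publication and a day-28 mortality difference, and the available text specifies no interim review of bowel ischemia. For an excess of 1 to 2 points, interim mortality testing gives about 1% to 5% chance per look of flagging harm, little above its 0.5% floor. A direct chi-square comparison gives about 8% to 37% at 1000 patients and 22% to 75% at 2000, somewhat less with Fisher's test. These figures rest on assumed rates by arm and on an illustrative 0.01 level, and they do not describe a review based on judgement. The conclusion does not extend to a very large, highly fatal excess. The validity of the primary analysis is unaffected. This is an inexpensive improvement in participant safety that the sponsor should make.

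**What to change.** In 4.5.2 and 7.4, state that at both interim analyses the existing independent committee also receives by-arm counts of bowel ischemia and liver dysfunction. Add nosocomial infections, marked as unadjudicated where the adjudication required by 4.3.2 is not complete. State that the committee may recommend pausing or stopping on safety grounds, with no formal boundary and no change to the mortality significance levels. If section 1.2 already gives a committee remit, align the three sections.

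Two supporting steps are needed. Confirm that the case-report form captures bowel ischemia in time for each look. Reconcile the ischemia definition in 4.1.2 with the description of the feared condition in the overview.

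The cost is one more table in each of two reports already planned, plus possibly a case-report-form item. No extra patients are needed. The downside is that the safety review rests on the committee's judgement, and the infection counts may be provisional.

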### 4.6 Data collection

All the study data are collected routinely in ICUs for the management of mechanically ventilated patients with shock.

#### Demographics and clinical data

- At inclusion: date of birth, sex, date of ICU admission, reason for ICU admission, McCabe and Knaus scores, chronic co-morbidities, body weight, height, BMI, and SOFA score
- at H24: SAPS II and SOFA score

---

- follow-up: date of final extubation, date of ICU discharge, date of hospital discharge (Acute care hospital), vital status at ICU discharge, and vital status at hospital discharge

Nutritional data, every day, *until extubation of the patient*: name of the enteral or parenteral preparation; target number of calories; volume and calories delivered each day; vomiting (yes/no every 4 hours, with the time of any vomiting episodes); decrease or discontinuation of nutritional support (yes/no); reason for decreasing or discontinuing nutritional support (vomiting, diarrhea, acute pseudoobstruction of the colon, other acute abdominal symptoms, abdominal complication, imaging study/other); presence, volume, and appearance of the stools (yes/no every 4 hours, exact volume in mL and, where applicable, qualitative description as normal/liquid/mucopurulent/mucous/bloody); and diarrhea with its presumed cause (intolerance to nutritional support, medication, *Clostridium difficile*, other).

Treatments given: Every day, *until extubation of the patient*: prokinetic agent (dose/24 h), polyethylene-glycol (dose/24 h), neostigmine (dose/24 h), sedation (dose/24 h and nature of the hypnotic and/or opioid agents), neuromuscular blockers (dose /24 h), catecholamines (dobutamine, noradrenaline, or adrenaline; yes/no regardless of duration and dose), renal replacement therapy (yes/no), antibiotics (yes/no), insulin (total dose/24 h), volume of IV fluids (total/24 h), and gastric anti-secretory agents (sucralfate, proton-pump inhibitors, histamine receptor antagonists, other).

#### Laboratory data

- D1: hemoglobin, leukocytes, platelets, Na, K, Ca2+, Ph, PaO2, PaCO2, pH, arterial lactic acid, bicarbonate, urea, creatinine, bilirubin, ASAT-ALAT, gamma-glutamyl transpeptidase, alkaline phosphatase, and total protein
- Daily from D1 to D7 (if extubation before D7: on the day of extubation then stop): PaO2, arterial lactic acid, bilirubin, ASAT-ALAT, gamma-glutamyl transpeptidase, alkaline phosphatase, glucose, protein, Na, K, Ca2+, Ph, creatinine, and SOFA
- Albumin, pre-albumin, transthyretin, and CRP on D1 and D7 or on the day of extubation

Nosocomial infections (one data-collection form per infection): VAP (date, organism, resistance profile), bacteremia (date, organism, resistance profile), intravascular catheter-related infection (date of the diagnosis, organism, resistance profile), urinary tract infection (date of the diagnosis, organism, resistance profile), soft tissue infection (date of the diagnosis, organism, resistance profile); and other (type, date of the diagnosis, organism, resistance profile).

Invasive devices: endotracheal tube (dates of insertion and removal), intravascular catheters (dates of insertion and removal), and urinary catheters (dates of insertion and removal)

#### Additional data collected during the ancillary studies

##### – Ancillary study 1

Plasma citrulline and I-FABP assays on D0, D3, and D8. Blood will be drawn by the nurse in charge of the patient as part of standard care. Each blood sample will be labeled with the number assigned to the patient, the first initial of the patient's last and first names, the patient's date of birth, the date and time of sample collection, and the number assigned to the sample.

For amino acid chromatography, the blood samples will be centrifuged within 2 hours after collection (4°C, 1900 rpm, 10 minutes) and the plasma stored at -70 °C at the study center.

For the I-FABP assay, the blood samples will be centrifuged (4°C, 1500 rpm, 15 minutes) and the plasma stored at -70°C until the analysis.

An accredited transporter will take the samples to the Biology Center of the Besançon Teaching Hospital, where they will be processed. The samples will be destroyed after the assays are performed.

##### – Ancillary study 2

D0, D3, and D8: pepsin and salivary amylase assays in all tracheal aspirates

The tracheal aspirate samples will be collected by the nurse in charge of the patient, according to standard practice. Each sample will be labeled with the number assigned to the patient, the first initial of the patient's last and first names, the patient's date of birth, the date and time of sample collection, and the number assigned to the sample. Each tracheal aspirate sample (about 1-2 mL per aspirate) will be stored at -20 °C at the biochemistry department of each

study center. An accredited transporter will take the samples to the Biology and Pathology Center of the Lille Teaching Hospital, under the responsibility of [name], [name], and [name], for blinded assays of pepsin and salivary amylase. Pepsin levels will be measured using an ELISA, under the responsibility of [name] and [name], at the Molecular Biochemistry-Biology Laboratory headed by Pr. [name], Biochemistry Department, Lille Teaching Hospital. The amylase assays will be performed under the responsibility of [name] at the Biochemistry, Proteins, and Predictive Biology Laboratory headed by Pr [name], Biochemistry Department, Lille Teaching Hospital. A colorimetric enzyme assay will be used. The level of salivary amylase will be computed as the difference between total and pancreatic amylase levels. The samples will be destroyed after the assays are performed.

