
	
 
▪ ICU stay length
 
▪ hospital stay length
 
▪ total time spent on mechanical ventilation
 
▪ mean change in body weight from admission to day 7 and to ICU discharge
 

OUTCOME MEASURES FOR THE ANCILLARY STUDIES	
 
▪ Ancillary study 1 
Primary outcome measure: Plasma citrulline level at H72
 
Secondary outcome measures: SOFA score; plasma levels of citrulline and I-FABP on D0, D3, and D8; proportion of patients whose plasma I-FABP is <math>\geq 100</math> pg/mL on D0, D3, and D8; proportion of patients whose plasma citrulline is <math>\leq 10</math> <math>\mu</math>L/L on D0, D3, and D8; mean plasma I-FABP; mean plasma citrulline; proportion of patients with at least one episode of bacteremia; proportion of patients with at least one episode of gastrointestinal intolerance; proportion of patients with at least one episode of diarrhea; in the enteral-nutrition group, cumulative calorie intake over the first 3 days and on D7; impossibility of administering enteral nutrition.
 
 
▪ Ancillary study 2 
Primary outcome measure: proportion of patients with abundant microaspiration (defined as a pepsin level <math>> 200</math> ng/mL in at least 30% of tracheal aspirates).
 
Secondary outcome measures: Salivary amylase levels in tracheal aspirates.
 
 

INCLUSION CRITERIA FOR STUDY PARTICIPANTS	
 
▪ invasive mechanical ventilation for an expected duration of at least 48 hours
 
▪ nutritional support started within 24 hours after intubation, or after ICU admission in patients intubated before ICU admission
 
▪ administration of a vasoactive agent (adrenaline, dobutamine, or noradrenaline) via a central venous catheter
 
▪ age older than 18 years
 
▪ informed consent to study participation
 
▪ coverage by one of the French statutory health insurance agencies
 

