NONINCLUSION CRITERIA FOR STUDY PARTICIPANTS	
 
▪ invasive mechanical ventilation started more than 24 hours earlier
 
▪ surgery on the gastrointestinal tract within the past month
 
▪ history of gastrectomy, esophagectomy, duodenopancreatectomy, gastric bypass or banding, or short bowel syndrome
 
▪ gastrostomy or jejunostomy
 
▪ specific diet
 
▪ active bleeding from the gastrointestinal tract
 
▪ dying patient – not-to-be-resuscitated order or other treatment limitation decision at ICU admission
 
▪ adult under guardianship
 
▪ pregnancy, recent delivery, or lactation
 
▪ patient admitted without his or her consent
 
▪ department of corrections inmate
 
▪ institutionalized patient
 
▪ prior inclusion in a randomized trial comparing early enteral nutrition to early parenteral nutrition and having mortality as the primary outcome measure
 
▪ contraindication to parenteral nutrition: known hypersensitivity to egg protein, soybean protein, or another component; inborn error in
 

	amino acid metabolism; severe familial dyslipidemia manifesting as hypertriglyceridemia
STRATEGIES / PROCEDURES	In both groups, nutritional support will be started within 24 hours after the initiation of mechanical ventilation. Calorie targets will be 20-25 Kcal/Kg/day during the first week then 25-30 Kcal/Kg/day starting on day 8. In the parenteral nutrition group, a switch to the enteral route will be possible after at least 72 hours of parenteral nutrition, provided the vasoactive agent(s) were stopped at least 24 hours earlier and the arterial lactic acid level is lower than 2 mmol/L; on day 7, all patients will be switched to enteral nutrition in the absence of an absolute contraindication to use of the enteral route. In the enteral nutrition group, supplemental parenteral nutrition may be added, starting on day 8, in patients with intolerance to enteral nutrition and inadequate calorie intakes. A written protocol for prescribing and delivering nutritional support will be available to ensure standardization across study centers.

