STRATEGIES / PROCEDURES SPECIFIC OF THE ANCILLARY STUDIES	
 
– Ancillary study 1 The assays on D0, D3, and D8 will be performed on part of the blood samples drawn for the standard care of these critically ill patients.
 
– Ancillary study 2 All tracheal aspirates (obtained routinely in patients receiving invasive mechanical ventilation) will be collected over the first 48 hours following randomization and stored at -20°. The aspirates will then be centralized at the Biology and Pathology Center of the Lille Teaching Hospital (Lille, France), where they will be used for quantitative assays of pepsin and salivary amylase.
 

NUMBER OF PATIENTS	1427 in each group, i.e., 2854 patients in all
NUMBER OF PATIENTS IN THE ANCILLARY STUDIES	
 
– Ancillary study 1 85 patients per group, i.e., 170 patients in all
 
– Ancillary study 2 94 patients per group, i.e., 188 patients in all
 

DURATION OF THE STUDY	
Inclusion period duration: 30 months
 
Duration of participation for each patient: duration of mechanical ventilation (final extubation), follow-up until hospital discharge
 
Total study duration: 36 months (30 months for inclusion plus 6 months for follow-up and data checking).

PLANNED TRIAL START DATE	September 3, 2012
EXPECTED IMPACT	If the study hypothesis is confirmed, early enteral nutrition will become the reference standard for initial nutritional support in mechanically ventilated patients with shock, and the result will be decreased morbidity and mortality rates and improved overall patient outcomes.

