#### 4.2.7 Patient follow-up

The following will be recorded until the patient is extubated: vital signs, nutrition monitoring data, laboratory tests, and data relevant to nosocomial infections. The patient will

be followed-up to hospital discharge, D28, and D90. At these time points, vital status will be recorded. Below is a flowchart of patient follow-up.

	Inclu-sion	Rando-mization	D0*	D1 to Dn	End of study	D28	D90
Eligibility: check inclusion and exclusion criteria	X						
Patient information and consent	X						
Randomization	X						
Demographics	X						
Characteristics			X				
Ventilation			X				
Laboratory tests			X	X*			
SOFA			X	X			
Nutritional evaluation			X	X			
Treatments used			X	X			
Daily calorie intake				X			
Nosocomial infections					X		
Final extubation						X	
Final discontinuation of nutritional support						X	
Survived / died					X	X	X

\*from time at inclusion to 11:59 pm

---

Design of the ancillary studies

---

### Ancillary study 1

The plasma citrulline and I-FABP assays on D0, D3, and D8 will be performed using blood drawn as part of the standard care of critically ill patients; the volume of each blood sample will be increased slightly (by about 2 mL) to allow these assays. For amino acid chromatography, blood will be drawn in a lithium heparin tube, which will be transported on ice as promptly as possible to the medical biochemistry laboratory. At arrival at the laboratory and within 2 hours after blood collection, the sample will be centrifuged (4°C, 1900 rpm, 10 minutes) and the plasma stored at -70 °C until the analysis.

The samples will be centralized at the Biology Center of the Besançon Teaching Hospital. After thawing and deproteinization, ion-exchange chromatography will be performed on a Hitachi L-8800 analyzer (Hitachi, Tokyo, Japan).

I-FABP will be assayed using a blood sample drawn into an EDTA tube, which will be taken as rapidly as possible to the medical biochemistry laboratory. At arrival at the laboratory, the sample will be centrifuged (4°C, 1500 rpm, 15 minutes) and the plasma stored at -70°C until analysis by ELISA (Hycult Biotech, Uden, The Netherlands) at the Biology Center of the Besançon Teaching Hospital.

### Ancillary study 2

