Tracheal aspiration will be performed according to standard practice in the study centers. All tracheal aspirates obtained within 48 hours after randomization for the NUTRIREA2 trial will be stored frozen at each study center. The frozen aspirates will be sent to the Biochemistry Department of the Lille Teaching Hospital (Dr. [name], Dr. [name], and Dr. [name]), where the pepsin and salivary amylase assays will be performed.

The measures taken to prevent microaspiration will comply with current recommendations and with standard practice in each study center. They will consist of the following:

- Endotracheal tube cuff pressure kept at about 25 cm H2O;
- Semi-recumbent patient position;
- Application of at least 5 cmH2O of positive end-expiratory pressure (PEP) in patients without contraindications;
- Daily evaluation of criteria for weaning off mechanical ventilation, to minimize the duration of mechanical ventilation;
- No routine prophylactic treatment of stress-induced ulcers; and
- Limited use of sedation and application of a sedation management protocol.

---

5.15 4.3 Description of measures taken to minimize and avoid biases

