#### *– Ancillary study 2*

The primary outcome measure is the proportion of patients with abundant microaspiration. We expect that the proportion of patients with abundant microaspiration will be 50% in the enteral-nutrition group and 30% in the parenteral-nutrition group. With the alpha risk set at 0.05, to obtain 80% power, 94 patients will be needed in each group (188 patients in all), with simple random sampling.

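### The aspirate collection window behind ancillary study 2's primary outcome is contradictory: first 48 hours in two places, D0, D3 and D8 in a third

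*Combined protocol and SAP*

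**What the plan says.** Three places in the combined protocol and SAP describe which tracheal aspirates are used in ancillary study 2.

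- Synopsis, procedures specific to the ancillary studies: aspirates "will be collected over the first 48 hours following randomization".
- Section 4.2.7, design of ancillary study 2: "All tracheal aspirates obtained within 48 hours after randomization for the NUTRIREA2 trial will be stored frozen at each study center".
- Section 4.6, additional data for the ancillary studies: "D0, D3, and D8: pepsin and salivary amylase assays in all tracheal aspirates". Just above, the same section gives the blood sampling of ancillary study 1 as "Plasma citrulline and I-FABP assays on D0, D3, and D8".

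The synopsis defines abundant microaspiration as pepsin above 200 ng/mL "in at least 30% of tracheal aspirates". Section 4.1.3 names the outcome without that definition. Neither place states a window. Section 7.2 expects 50% (enteral) against 30% (parenteral) and concludes that "94 patients will be needed in each group (188 patients in all), with simple random sampling"; it names no window either.

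On the parenteral arm, the synopsis says that "a switch to the enteral route will be possible after at least 72 hours of parenteral nutrition", subject to hemodynamic conditions. Without a contraindication, the default switch comes on day 7 (synopsis) or day 8 (sections 4.2.4 and 6.1).

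**The concern.** A patient counts as positive according to the share of his or her aspirates that exceed the pepsin threshold. Which aspirates are eligible therefore sets both the numerator and the denominator. Two schedules that select largely different aspirates give two different primary outcomes under one name.

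The two schedules also differ in what they compare. The first 48 hours fall while each arm is on a single route. A schedule that reaches D8 includes days on which a parenteral patient may already be fed enterally, and on which only patients still alive and intubated can supply a sample. If centers follow different sections, the outcome is not the same across centers, and aspirates that were never kept cannot be recovered.

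**Working it through.** **1. Put both schedules on one clock.** The footnote to the follow-up flowchart (section 4.2.7) defines D0 as "from time at inclusion to 11:59 pm". Let L be the length of D0 in hours (at most 24), and take randomization as simultaneous with inclusion, since the flowchart puts both in the same column.

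| Day | Hours after inclusion | Hours inside the 48-hour window |
|---|---|---|
| D0 | 0 to L | L |
| D1 | L to L+24 | 24 |
| D2 | L+24 to L+48 | 24 − L |
| D3 | L+48 to L+72 (starts at 48–72, ends at 72–96) | 0 |
| D8 | L+168 to L+192 (starts at 168–192) | 0 |

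The schedules overlap only on D0. D1 and D2, which section 4.6 omits, hold 24 + (24 − L) = 48 − L hours, that is, at least 24 of the 48.

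**2. Overlay the switch rules.** Parenteral feeding is assigned by randomization and must run for at least 72 hours, so the 48-hour window closes before any permitted switch. D3 contains at most L hours beyond hour 72. Even then, section 4.2.4 requires 24 hours without vasoactive amines and lactate below 2 mmol/L, so only a few late D3 samples can be affected. D8 starts at hour 168 or later, when a parenteral patient may have switched already or may be due to switch that day.

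**3. Reproduce the plan's sample size.** Inputs from section 7.2: p₁ = 0.50, p₂ = 0.30, alpha 0.05, power 80%. Section 7.1.5 specifies a chi-square test. Sidedness is not stated for this study; two-sided is assumed.

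n = [1.960·√(2p̄q̄) + 0.842·√(p₁q₁ + p₂q₂)]² / (p₁ − p₂)², with p̄ = 0.40 and q̄ = 1 − p̄

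= [1.960·√0.48 + 0.842·√0.46]² / 0.04 = 93 per group.

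Using 2p̄q̄ in both terms gives 94.2. Power at 94 per group is Φ{[0.20·√94 − 1.960·√0.48] / √0.46} = 80.4%. The stated 94 is reproduced.

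**4. Illustrate dilution.** Suppose a fraction f of parenteral patients show the enteral rate because some of their aspirates were taken after a switch. Then p₂ = 0.30 + 0.20f. Hold p₁ at 0.50 and n at 94 per group, and use the same formula:

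| f (assumed) | p₂ | Power |
|---|---|---|
| 0 | 0.30 | 80.4% |
| 10% | 0.32 | 71% |
| 25% | 0.35 | 55% |
| 50% | 0.40 | 28% |

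The documents give no value for f, no switching rate and no share still intubated on D8.

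**The case against.** The strongest reply is that two of the three places agree on 48 hours, that section 4.2.7 is as operational as section 4.6, and that the odd line has the same days as ancillary study 1 immediately above it. It may simply have been carried over. That is plausible, but it is an inference, and the plan has no rule of precedence. It also means that a reader cannot assume that centers will follow section 4.6.

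Four stronger readings are tempting, and the documents do not support them.

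- *The sample size was built on the 48-hour outcome.* Section 7.2 ties its 50% and 30% to no window and no source.
- *D8 samples cannot compare the routes at all.* The switch has exceptions: a contraindication to enteral feeding, or the physician's decision to continue parenteral nutrition (section 6.1). Under section 4.2.4 the default switch falls on day 8 itself. D0 precedes any switch, and D3 is barely affected.
- *Patients who die or are extubated early drop out of the outcome.* They still contribute D0 aspirates; what they lose is later samples.
- *Power will fall to 55% or 28%.* Those figures need a quarter or a half of parenteral patients to take on the full enteral rate, although many of their pooled aspirates would predate a switch. Another window could also move the enteral rate, which the illustration holds fixed.

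What the reply leaves standing is the contradiction itself, and the fact that only one of the two windows lies wholly before any permitted switch.

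**Conclusion.** The plan is wrong as written on this point: it gives two incompatible collection windows for the primary outcome of ancillary study 2, and no other text reconciles them. This rests on comparing the sections and on the D0 footnote, not on any assumed rate.

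The section 4.6 version is the weaker one for comparing routes, because it leaves out at least half of the first 48 hours, makes later sampling depend on survival and continued intubation, and admits some post-switch aspirates in the parenteral arm. The size of the dilution cannot be determined from the documents; the range in step 4 shows its direction and how it could scale, and is not a forecast. The sample size of 94 per group stands. The effect is confined to a 188-patient ancillary study.

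**What to change.** In section 4.6, replace the D0/D3/D8 line for ancillary study 2 with the window already given in the synopsis and section 4.2.7: all aspirates from the first 48 hours after randomization. State the same window in the outcome definition in the synopsis and in section 4.1.3, and repeat there the pepsin threshold and the 30% rule, which section 4.1.3 lacks. If sampling has started, record for each center which schedule was followed.

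Separately, the day 7 and day 8 wordings of the default parenteral-to-enteral switch (synopsis against sections 4.2.4 and 6.1) must be reconciled by the sponsor.

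The cost is one corrected line and two short additions, with no change to the sample size. Whether laboratory work rises or falls is not known. A patient intubated through D8 would have L + 48 hours of sampling under section 4.6 (48 to 72 hours), and one extubated before D8 at most L + 24 (no more than 48), so the balance depends on extubation times that the documents do not give.
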